8.8 Description of Methods (or include in separate document)

Check to indicate that the Methods are described in an attached file →

Each extraction socket will receive one 5 X 5 X 8mm or 5 X 5 X 10mm graft cube (research) with no attempt to fill the entire socket. No wound dressing or membrane will be used to cover the bone graft material as both materials can be used alone. All extraction sockets will be sutured with Vicryl 4.0 mattress suture which will be removed approximately 2 weeks (\pm 1 week) after the procedure as per standard of care. All patients will be prescribed an oral antibiotic after the procedure either Amoxicillin 500mg three times per day for 7 days, or if they are allergic to penicillin/amoxicillin they will be prescribed Clindamycin 300mg three times per day for 7 days as per standard of care.

In keeping with the protocol our study group has used several times before, the plan will be to extract non-molar teeth and graft with the test/control materials. Each subject will provide a single non-molar tooth site for study treatment. Following approx. 14 weeks of healing, we will harvest a core biopsy at the time of implant placement. The core biopsy will then be evaluated for the primary outcomes: % vital bone formation, % residual graft material, and % "CT/other" (fibrous tissue and marrow space). We will also evaluate the following secondary outcomes using a custom measuring stent for each subject: change in ridge width; change in buccal ridge height, and change in lingual ridge height. During the 14-week healing period, subjects will be followed up with biweekly and monthly visits as per standard of care, to evaluate healing.

A detailed visit by visit outline is provided below:

Step-by-Step Methods: All the procedures are routinely performed in the graduate periodontics clinic as part of standard care. The methodology is the same previous studies of our group HSC20130470H, HSC20150708H, HSC20170339H, HSC20170267H, among others.

Visit 1 - Screening examination:

If a patient presents at a consultation appointment at the graduate periodontics clinic with a non-molar tooth (incisors, canines, premolars) that needs to be extracted and replaced with a dental implant, the treating doctor will provide:

- Explanation to the patient of the purposes of the study and the planned procedures related to the study.
- Explanation to the patient of the risks, benefits and possible complications of participation in the study.

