One measurement stent will be fabricated to facilitate clinical ridge measurements. A clear suck-down resin measuring stent will be fabricated in the laboratory to allow standardization of the location of clinical measurements of ridge width and height through small holes that will be placed in the stent at the time of tooth extraction.

The width of keratinized tissue will be recorded clinically to the nearest 0.5mm using a periodontal probe at the mid-buccal and mid-lingual sites of the tooth to be extracted.

A pre-operative periapical radiographic image will be taken before the extraction as per standard of care (if not already available).

At the time of surgery, local anesthesia will be administered. Conscious sedation will be administered according to patient need and investigator preference, per standard care. Buccal and lingual flaps will be minimally reflected to a point up to 3mm apical to the bony crest.

Prior to tooth extraction, the clinical measuring stent will be placed and measurements of ridge width and ridge height will be taken and recorded to the nearest 0.5mm. Ridge width will be measured to the nearest 0.5mm using a ridge caliper at a point approximately 4mm apical to the facial and lingual bony crest through small holes created in the stent at those locations. Ridge height will be measured to the nearest 0.5mm through two holes in the occlusal aspect of the stent – one hole directly above the facial bony crest and another hole directly above the lingual bony crest. This stent will be retained for use during the subsequent implant placement surgery.

Tooth extraction will be performed as atraumatically as possible. Following tooth extraction, a final determination of enrollment into the study will be conducted based on the integrity of the buccal bone wall plate at the extraction site. If the buccal plate is intact, defined as no bony dehiscence greater than 50% of the socket depth, the patient will remain enrolled in the study.

Conversely, if the buccal plate integrity has not been maintained (bony dehiscence >50%) the patient will be exited from the study and standard care therapy will be delivered to the patient.

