Approximately 16 weeks (\pm 2 weeks) after the extraction, implant surgery will be performed (standard of care). The width of keratinized tissue will be measured at the prospective implant site. A piece of floss will be run over the keratinized tissue and cut to the width of keratinized tissue, i.e. from the mucogingival junction (MGJ) on the buccal to the MGJ on the lingual. The floss will be then measured with a ruler to the closest 0.5mm.

After local anesthesia (and conscious sedation if requested), the patient will undergo implant placement surgery at the previously extracted tooth site and if required simultaneous guided bone regeneration (GBR) will be performed as per standard care. First, the individual subject's measuring stent and caliper will be used to determine the ridge width and ridge height at the same locations as done in the tooth extraction/grafting surgery visit. During the implant bed preparation, a hollow drill will be used to allow retrieval of a bone core which will be collected and stored in formalin and subsequently examined histologically and outcomes including percentages of new bone formation, residual graft and connective tissue/other will be recorded.

- During the implant placement procedure, the following data will be recorded per standard care:
- Bone quality according Lekholm and Zarb (1985) classification
- Absence/Presence of bone defect, including dehiscence or crater like defect. If present, at what site(s) (Buccal, Mesial, Lingual, Distal) and what are the respective depth and width of these defects.
- Absence/Presence of bone fenestration. If present what is the size of the fenestration in height and width.
- Was additional bone grafting needed in case of thin bone or dehiscence of threads? Yes/No

Subject participation ends at the time of implant placement. However, standard care post-operative visits will be provided after implant placement. Generally, one or two post-operative visits will be provided during the first month after implant surgery to insure adequate healing.

9. Preparation/Handling/ Storage/Accountability of Investigational Drug, Biologic, or Device

N/A - This study does not include any investigational products (e.g. drugs, devices or biologics)

N/A - An Investigator Brochure is attached

N/A - A Drug/Device Manual is attached

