10.1. Measures to Minimize Bias: Randomization and Blinding

This section should contain a description of randomization and blinding procedures (if applicable to the study design). It should include a description or a table that describes how study participants will be assigned to study groups, without being so specific that blinding or randomization might be compromised. Plans for the maintenance of trial randomization codes and appropriate blinding for the study should be discussed. The timing and procedures for planned and unplanned breaking of randomization codes should be included. Include a statement regarding when unblinding may occur and who may unblind. Provide the criteria for breaking the study blind or participant code. Discuss the circumstances in which the blind would be broken for an individual or for all participants (e.g., for serious adverse events (SAEs)). Indicate to whom the intentional and unintentional breaking of the blind should be reported.

22 envelopes will be prepared for each arm in a simple randomization 1:1 ratio, sealed and shuffled. The faculty staffing the procedure will draw an envelope from the stack prior to the surgical procedure appointment. Since the outcome of the study is the histologic healing, blinding of the surgeon is not necessary.

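### Section 10.1 excuses an unblinded surgeon because the outcome is histologic, but no masking is stated for the reader of the cores, and the reason does not reach the three ridge outcomes

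*Combined protocol and SAP*

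**What the plan says.** Section 10.1 describes sealed, shuffled envelopes, 22 per arm, and then says: "The faculty staffing the procedure will draw an envelope from the stack prior to the surgical procedure appointment". Its one sentence on blinding is: "Since the outcome of the study is the histologic healing, blinding of the surgeon is not necessary".

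On the primary outcomes (percentages of vital bone, residual graft and CT/other), section 8.8 says: "The core biopsy will then be evaluated for the primary outcomes". Under Visit 5 it describes a bone core "which will be collected and stored in formalin and subsequently examined histologically". It does not say who reads the core, how it is labelled, or whether the reader knows the arm.

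On the ridge outcomes, section 8.8 says: "We will also evaluate the following secondary outcomes using a custom measuring stent for each subject". The baseline reading belongs to Visit 2: "Prior to tooth extraction, the clinical measuring stent will be placed and measurements of ridge width and ridge height will be taken", to the nearest 0.5 mm. The second reading is at Visit 5, where "the individual subject's measuring stent and caliper will be used to determine the ridge width and ridge height". Neither visit names the measurer. Section 10.2 adds that the faculty who staff residents can verify the measurements.

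**The concern.** A histologic endpoint makes an unblinded surgeon acceptable when the assessment is separated from the surgery and made without knowledge of the arm. The plan relies on that separation without providing for it. Sorting tissue into vital bone, residual graft or other calls for judgement, and a reader who knows the product could lean one way.

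The reason also treats histology as the only outcome. Half of the six named outcomes are clinical measurements taken at the two operations, where product knowledge is most likely to be present. They are change scores, so knowledge of the arm at either reading can affect them.

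A systematic reading difference between arms enters the comparison exactly as a treatment effect would. The analysis in section 12.4, a two-sample t-test, cannot tell the two apart, and adding patients does not shrink it.

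**Working it through.** **Setting the passages side by side**

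| Outcome set | When read | Masking stated | Does the reason in 10.1 cover it? |
|---|---|---|---|
| Three histologic percentages (primary) | After Visit 5, from the core | None | Only if the reader is masked |
| Three ridge changes (secondary) | Visit 2 and Visit 5, at surgery | None | No, they are not histologic |

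**Order of events at Visit 2.** Section 10.1 has the envelope drawn before the surgical appointment. Section 8.8 has the baseline width and heights measured during that appointment, before extraction. The baseline reading therefore follows the draw. The plan does not say when the drawn envelope is opened, so nothing keeps the allocation unknown while the baseline is read.

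**Who may know the arm.** The supervising faculty draw the envelope (10.1), and faculty staffing residents are able to verify measurements (10.2). Taken together, these make it likely that someone aware of the arm takes or checks the ridge readings.

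**The plan's own figures.** The plan gives no figure for assessor bias. Its sample-size figures (12.2) are used here only to fix the number per arm.

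- Dropout: 14 / (1 − 0.30) = 20 per group; the plan enrols 22, and 22 × 0.70 = 15.4, taken as 15 evaluable per arm.
- Power: the stated 88.5% at 14 per group and 1 SD is reproduced if the Mann-Whitney test is credited with a relative efficiency of 1.5 (a Laplace distribution, which the plan does not name). Then 14 × 1.5 = 21, and the two-sided t-test power at 21 per group is 88.5%. Nothing below depends on this.

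**Illustration of size.** Inputs: two-sided 5% t-test (12.4), *n* per arm as above, no true difference, and an assumed shift of *b* SD between arms that comes only from reading. The test statistic then has a noncentral t distribution with

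- degrees of freedom = 2*n* − 2
- noncentrality = *b* × √(*n*/2)

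and the false-positive rate is the probability that its absolute value exceeds the usual critical value. For *n* = 15, √(15/2) = 2.739, so *b* = 0.25 gives noncentrality 0.685 and *b* = 0.5 gives 1.369, on 28 degrees of freedom.

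| Assumed shift *b* | 14 per arm | 15 per arm | 22 per arm |
|---|---|---|---|
| 0 | 5.0% | 5.0% | 5.0% |
| 0.10 SD | 5.8% | 5.8% | 6.2% |
| 0.25 SD | 9.8% | 10.1% | 12.8% |
| 0.50 SD | 24.7% | 26.2% | 36.7% |

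The rate rises from left to right: a larger sample detects the artefact more often. Masking changes neither the sample size, nor alpha, nor the planned power.

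**The case against.** The strongest reply is that the plan is silent here rather than wrong. Section 10.1 waives blinding for the surgeon only. Section 8.8 says the methods match the group's earlier studies, and no slide preparation or histomorphometry method is described at all, so masked reading may simply be local routine left unwritten. That stands against one tempting reading: a reader might infer that blinding as a whole is waived, or that the cores will be read with the arm known. The documents do not say so. What they support is that masking is not stated, while the reason given in 10.1 depends on it.

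A reader might likewise infer that the unblinded surgical team takes all the ridge readings. The text is in the passive voice, names no measurer, and does not say that the same operator attends Visit 5, about 16 weeks after extraction. The inference is reasonable, but it is an inference.

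Two features limit discretion in the ridge readings: the stent fixes the measurement location, and section 10.2 provides for training. Neither hides the arm.

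Blinding the surgeon is plausibly impractical, since the surgeon handles the named product. That stands too, and nothing here asks for it.

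Finally, coding the slides may mask them only in part if the two residual grafts look different under the microscope. The documents do not settle this. Coding would still stop the label itself from steering the reading.

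**Conclusion.** The point holds in a limited form. The one reason given for an unblinded surgeon is sound for the histologic outcomes only if the core reader is masked, which is not stated. It does not apply to the three ridge outcomes, for which no masked examiner is named and whose baseline follows the envelope draw. All six primary and secondary outcomes are therefore left without stated protection against assessor bias.

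The false-positive rates of about 10% (0.25 SD) and 26% (0.5 SD) at 15 per arm show how sensitive a trial of this size is. They rest on assumed shifts, because the documents give no size for assessor bias. A reader might infer from them that this trial's results will be biased by that much, or at all; the documents do not support that.

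A reader might also suppose that coded cores would settle the whole matter at no cost. Coding cannot affect a caliper reading, so the ridge outcomes need their own step. The documents give no basis for saying that the cost is nil, though it should be low.

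**What to change.** Amend the sentence in 10.1 rather than delete it, since it is the plan's only disclosure that the surgeon is unblinded. It should say that the surgeon is unblinded, and section 10.1 should then add the following.

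- **Histology:** core containers and slides carry the study number only, and the histomorphometry reader has no access to the allocation until all readings are locked.
- **Baseline ridge readings (Visit 2):** stent readings are taken and recorded before the envelope is opened.
- **Follow-up ridge readings (Visit 5):** stent readings are recorded before the Visit 2 record, with the group and baseline values, is consulted. Where the existing roster allows, they are taken by a team member who did not place the graft.

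The Visit 5 order of recording does not mask someone who placed the graft or drew the envelope. The separate examiner is the stronger step, and where none is available the report should say so.

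The cost is relabelling of containers and slides, a few sentences in the protocol, and a fixed order of recording at two visits. No added staff or procedure is required. If the group already reads cores masked, the histology line merely records it. The remaining weakness is that slide masking may be partial if the two grafts can be told apart.

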10.2. Study Intervention Compliance

Define how adherence to the protocol (e.g., administration of study intervention, use of device,) will be assessed, and verified (if applicable, e.g., plasma assays, electronic monitoring devices, daily diaries).

Patients will need to be present at each scheduled visit. Failure to attend any of the visits will result in exit from the study. All providers placing test and control materials as part of the study intervention will be trained and provided with detailed instructions to ensure methods are consistent and in compliance with the protocol. All faculty staffing residents are familiar with the study protocol and are able to verify the results of the procedure and measurements taken.

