After extraction, the number of bony walls in each socket will be recorded along with the presence of any bony dehiscences or fenestrations. Buccal and lingual flap elevation will be minimized and will extend no more than 2-3mm beyond the bony crest on the facial and lingual surfaces. The buccal plate thickness will be measured using an Iwanson gauge positioned perpendicular to the inner wall of the extraction socket. One beak of the gauge will be placed within the extraction socket 1.0mm apical to the alveolar bone crest. The other beak will be placed on the external bone surface. This buccal plate thickness measurement will be recorded to the nearest 0.1 mm.

The socket will be thoroughly debrided, a 5 X 5 X 8 mm or 5 X 5 X 10 mm bone graft cube of either 90% bovine derived xenograft granules and 10% porcine collagen (Bio-Oss® Collagen, Geistlich, Inc.) or a resorbable sponge-like matrix of 80% hydroxyapatite and 20% sugar cross-linked porcine collagen (Ossix™ Bone, Datum Dental Ltd) will be soaked in patient's blood and inserted in the socket. No attempt will be made to completely fill the socket as the materials expand after they contact fluids. No membrane or wound barrier will be placed over the graft in either group. Vicryl 4.0 sutures will be placed over the graft material to secure it in place as part of standard of care. Primary closure will not be attempted.

Visit 3 - Post-operative visit

The post-operative visit after extraction/ridge preservation will be scheduled approximately 3 weeks (± 1 week) after the procedure. If needed, an optional POT visit may be scheduled before this visit, per standard care and as determined by patient need.

Visit 4 - Pre-implantation:

Approximately 3 months after the extraction (\pm 2 weeks) a CBCT of the prospective implant site may be taken as needed per standard care. The implant surgery will ensue within 2 weeks (\pm 2 weeks). The CBCT is not part of the study but rather standard of care.

Prior to surgery, pregnancy status will be confirmed verbally. An over the counter pregnancy test will be provided if pregnancy status is unknown or suspected (research). A negative result is required to continue being in the study.

Visit 5 - Implant placement:

Prior to surgery, pregnancy status will be confirmed verbally. An over the counter pregnancy test will be provided if pregnancy status is unknown or suspected (research). A negative result is required to continue being in the study.

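### Section 10.2 exits a patient for missing any visit, so a patient who misses only Visit 3 or Visit 4, where no primary or secondary outcome is recorded, forfeits an obtainable bone core

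*Combined protocol and SAP*

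**What the plan says.** Section 10.2 sets an attendance requirement, "Patients will need to be present at each scheduled visit", and its consequence, "Failure to attend any of the visits will result in exit from the study". It provides no exception and no make-up visit.

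Section 8.8 (Description of Methods) shows what each visit supplies:

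- **Visit 2:** extraction, baseline ridge measurements and the single graft placement.
- **Visit 3:** "The post-operative visit after extraction/ridge preservation will be scheduled approximately 3 weeks", with a window of 1 week either side. No measurement is listed.
- **Visit 4:** a CBCT if needed, of which the protocol says "The CBCT is not part of the study but rather standard of care", and a pregnancy check: "A negative result is required to continue being in the study". The same check is repeated at Visit 5.
- **Visit 5:** implant placement, described as standard of care. The core is taken here: "During the implant bed preparation, a hollow drill will be used to allow retrieval of a bone core which will be collected". The follow-up ridge data are also taken here: "measuring stent and caliper will be used to determine the ridge width and ridge height at the same locations".

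The core is the source of the primary endpoints: "The core biopsy will then be evaluated for the primary outcomes: % vital bone formation, % residual graft material", together with the connective tissue/other fraction.

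Three other sections bear on the point. Section 12.2 counts only fully compliant patients towards its target of 14 per group and enrols 22 per group against a 30% dropout. Section 12.3 analyses participants who complete the study intervention, without saying whether that means receiving the graft or finishing the study. Section 11.2 says that all participating patients will be followed to study completion or until an adverse reaction resolves.

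**The concern.** The exit rule does not distinguish visits that supply outcome data from visits that do not. Missing Visit 5 loses the core whatever the rule says. Missing only Visit 3 or Visit 4 loses no primary or secondary outcome, yet the rule removes the patient before the one visit that matters for the primary analysis. The plan thus creates missing primary data that it could have collected.

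Two things are at stake. The first is precision, in a trial of 44 patients. The second is the basis of the comparison: exit happens after randomisation and depends on patient behaviour, so the patients analysed are selected on attendance. If attendance were related to how the site heals under one graft, the selection could bias the result. Nothing in the documents shows such a link.

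Section 12.3 does not repair this. Even if completing the intervention means only having received the graft, a patient who exited before Visit 5 has no core to analyse.

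**Working it through.** **Inputs.** 22 enrolled per arm, 30% loss, 14 per group required, a 1 SD difference and stated power of 88.5% by Mann-Whitney (Section 12.2). Two-sided 5% level and two-sample *t*-test (Section 12.4). The documents do not say how much of the 30% is due to a missed Visit 3 or 4 alone. Call that share *f*; it is an assumption and is varied below.

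**The plan's own figure.** The stated 88.5% at 14 per group is not reproduced. Two-sided power at n = 14 is 72.1% for the *t*-test and 70.0% for Mann-Whitney (*t*-test power at an effective n of 14 × 3/π). At n = 22 the Mann-Whitney figure is 88.5%, so the stated power matches the enrolled number, not the 14 completers. This is a separate matter for Section 12.2. It explains why the starting power below is low, and Section 10.2 is not its cause.

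**Route 1: a share of the planned loss.** If patients lost only through an interim visit are kept:

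- n per arm = 22 × (1 − 0.30 × (1 − *f*))
- power: two-sided noncentral *t*, difference 1 SD, 2n − 2 degrees of freedom
- 95% CI half-width in SD units = t(0.975, 2n − 2) × √(2/n)
- extra cores over both arms = 2 × 22 × 0.30 × *f*

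For *f* = 0: n = 22 × 0.70 = 15.4 and half-width = 2.046 × √(2/15.4) = 0.737 SD. For *f* = 0.25: n = 22 × (1 − 0.225) = 17.05 and extra cores = 44 × 0.30 × 0.25 = 3.3.

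| Assumed *f* | n per arm | Power for 1 SD | Half-width (SD) | Narrower than at *f* = 0 | Extra cores of 44 |
|---|---|---|---|---|---|
| 0 | 15.40 | 0.765 | 0.737 | 0% | 0 |
| 0.05 | 15.73 | 0.774 | 0.729 | 1.2% | 0.7 |
| 0.10 | 16.06 | 0.783 | 0.721 | 2.3% | 1.3 |
| 0.25 | 17.05 | 0.808 | 0.698 | 5.4% | 3.3 |
| 0.50 | 18.70 | 0.845 | 0.664 | 10.0% | 6.6 |
| 0.75 | 20.35 | 0.875 | 0.634 | 14.0% | 9.9 |

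**Route 2: without the 30%.** Assume instead that each of Visits 3, 4 and 5 is missed independently with probability *m*, and that nothing else causes loss. With the rule, a fraction (1 − *m*)³ supplies a core; without it, (1 − *m*). Cores lost to the rule = 44 × [(1 − *m*) − (1 − *m*)³].

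| Assumed *m* | n per arm with rule | n per arm without | Cores lost of 44 | Power with rule | Power without |
|---|---|---|---|---|---|
| 0.02 | 20.7 | 21.6 | 1.7 | 0.881 | 0.894 |
| 0.05 | 18.9 | 20.9 | 4.1 | 0.848 | 0.884 |
| 0.10 | 16.0 | 19.8 | 7.5 | 0.782 | 0.865 |

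**Margin against the target of 14.** Expected retention under the plan is 15.4 per arm, above 14. That is an average: with 30% independent loss, the chance that at least 14 of 22 remain is 81.4% in one arm and 0.814² = 66.2% in both.

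**The case against.** The strongest case against is about size. Every figure rests on an assumed share or rate. The visit windows and the optional extra post-operative visit allow rescheduling before a visit counts as missed. The 30% must also cover exits for dehiscence found after extraction, pregnancy exits and missed Visit 5, so the upper rows of the first table look unlikely. Section 12.2 has budgeted for full compliance, and expected retention exceeds its own target. All of this stands. It limits what can be said about the effect. It does not give a reason to discard a core that can be taken.

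The sponsor may also want attendance for its own sake. Suture removal (about 2 weeks, ± 1) overlaps the Visit 3 window, infection counts towards the 5% rule in Section 11.1, and Visit 4 carries a continuation requirement. These are reasons to press for attendance and to record a missed visit. Exiting the patient does not recover the missed check, and the pregnancy check recurs at Visit 5.

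The list of visits is uncertain too. The Schedule of Activities is a separate attachment, and Section 8.8 also mentions biweekly and monthly healing visits. If those count as scheduled, the exit rule reaches further than Visits 3 and 4.

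Finally, the wording of Section 12.3 is unclear whatever Section 10.2 says. That is correct, but the two must be edited together, or patients retained under a revised Section 10.2 could still be left out of the analysis.

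**Conclusion.** The concern holds, and the plan should be changed. As written, Section 10.2 discards obtainable primary and secondary data after randomisation, for missing visits at which none of those data are collected. This follows from the text and does not depend on any power figure.

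The size cannot be derived from the documents and may be small: nothing at *f* = 0, about one core at 5% to 10%, and 3.3 cores with a 5.4% narrower interval at 25%. The per-visit assumption of 2% to 10% gives 1.7 to 7.5 cores. Bias by graft is a possibility, not a finding. The case for acting is that the loss is avoidable and the remedy is nearly free.

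**What to change.** **Section 10.2.** Replace the exit sentence with wording such as: *A missed interim visit (Visit 3 or Visit 4) is recorded as a protocol deviation with its reason; the patient stays in the study for the core and ridge measurements at Visit 5.* Check which visits count as scheduled against the Schedule of Activities, and state the status of the biweekly and monthly healing visits. Leave the existing dehiscence and pregnancy exits unchanged.

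**Section 8.8, Visit 4.** Reconcile the pregnancy requirement, which is repeated at Visit 5, with the case of a missed Visit 4, so that the text says how the requirement is met then.

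**Section 11.2.** Align the follow-up statement with the revised Section 10.2; an automatic exit does not fit follow-up to completion.

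**Section 12.3.** Define the primary set as all randomised, grafted patients with an evaluable core (for ridge outcomes, a Visit 5 measurement), analysed in the assigned arm whatever interim visits were missed. Keep the visit-compliant set as a sensitivity analysis. The primary set still depends on reaching implant surgery, so report missing cores with reasons by arm.

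**Cost.** Wording changes only, with no new visits or patients. Under the 5% to 75% assumption, about 0.7 to 10 more cores and sets of stent measurements are processed, at surgery that is already standard of care. The downsides are that a few less compliant patients enter the primary set, and that a missed Visit 3 check stays unrecorded, as it does under the present rule.
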